13.1.6. Unanticipated Serious Adverse Device Effect

An unanticipated serious adverse device effect (USADE) is any serious adverse effect on health or safety or any life-threatening problem or death caused by, or associated with, a device, if that effect, problem, or death was not previously identified in nature, severity, or degree of incidence in the investigational plan or application (including a supplementary plan or application), or any other unanticipated serious problem associated with a device that relates to the rights, safety, or welfare of subjects. A USADE is a serious adverse device effect, which by its nature, incidence, severity or outcome has not been identified in the current version of the Investigator's Brochure.

13.1.7. Life Threatening

An AE is considered “life-threatening” if, in the view of the Investigator or Sponsor, it places the subject at immediate risk of death from the AE *as it occurred*. It does not include an AE that, had it occurred in a more severe form, might have resulted in death.

13.1.8. Serious, Unexpected, Suspected Adverse Reaction

All serious, unexpected, and suspected adverse reactions (SUSARs) must be reported by the Sponsor. Of note, in the US, the Sponsor must report an AE as a SAR only if there is evidence to suggest a causal relationship between the drug and the AE.

13.2. Severity and Causality Assessment for Adverse Events

13.2.1. Severity

Severity of an AE will be defined from the qualitative assessment of the degree of intensity of the event as determined by the Investigator or as reported by the subject. The assessment of severity is made irrespective of drug relationship or seriousness of the event and should be evaluated according to the following scales:

- 1 = Mild - Discomfort noticed, but no disruption to daily activity
- 2 = Moderate - Discomfort sufficient to reduce or affect normal daily activity
- 3 = Severe - Inability to work or perform normal daily activity

13.2.2. Causality Assessment for Adverse Events

The Investigator or designee is responsible for assessing the relationship between AEs and the investigational product. Additionally, the Investigator or designee is responsible for providing appropriate treatment for the event and for adequately following the event until resolution. The clinical Investigator or responsible designee should determine the investigational product relationship using the following explanations:

Not related: An AE that is clearly and incontrovertibly due to extraneous causes (disease, environment, other drugs etc.)

Unlikely related: An AE may be considered unlikely related if:

- Event or laboratory test abnormality, with a time to drug intake that makes a relationship improbable (but not impossible)
- Disease or other drugs provide plausible explanations

Possibly related: An AE may be considered ‘possibly related’ if it meets at least 2 of the following criteria:

- It follows a reasonable temporal sequence from administration of investigational product.
- It may readily have been produced by the subject's clinical state or by environmental or toxic factors.
- It follows a known response pattern to investigational product.

Related: An AE that is considered to be related to investigational product with a high degree of certainty. An AE may be considered probably related if it meets all of the following criteria:

- It follows a reasonable temporal sequence from administration of investigational product.
- It cannot be reasonably explained by the known characteristics of the subject's clinical state.
- It follows a known pattern of response to investigational product treatment.
- It reappears upon re-challenge.

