13.1.4. Suspected Adverse Reaction

A suspected adverse reaction (SAR) is an AE for which there is a reasonable possibility that the investigational product caused the AE. For the purposes of IND safety reporting, possibility means there is evidence to suggest a causal relationship between the investigational product and the AE. Suspected adverse reaction implies a lesser degree of certainty about causality than adverse reaction, which means any AE caused by an investigational product.

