13.1.5. Serious Adverse Event or Serious Adverse Reaction

A SAE or SAR is considered serious if, in the view of either the Investigator or Sponsor, it results in any of the following outcomes:

- Death
- A life-threatening AE
- Inpatient hospitalization or prolongation of existing hospitalization
- A persistent or significant incapacity or substantial disruption of the ability to conduct normal life functions, or
- A congenital anomaly/birth defect

Important medical events that may not result in death, be life-threatening, or require hospitalization may be considered serious when, based upon appropriate medical judgment, they may jeopardize the subject and may require medical or surgical intervention to prevent one of the outcomes listed in this definition. Examples of such medical events include allergic bronchospasm requiring intensive treatment in an emergency room or at home, blood dyscrasias or convulsions that do not result in inpatient hospitalization, or the development of drug dependency or drug abuse. A planned hospitalization for pre-existing condition, or a procedure required by the protocol, without a serious deterioration in health, is not considered to be a SAE.

If the subject develops respiratory failure, as defined in this protocol, it will be considered an SAE. This classification of serious events includes device deficiencies that might have led to a SAE if (a) suitable action had not been taken; or (b) intervention had not been made; or (c) circumstances had been less fortunate.

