13.6.2 Adverse Events

Treatment-Emergent Adverse Events (TEAEs) are defined as any AEs with an onset date on or after the date of the first dose of IP or any worsening of a preexisting medical condition/AE with onset after the start of IP and throughout the study. An AE leading to treatment discontinuation is defined as an AE where action taken on study drug is Drug Withdrawn. AEs will be coded using the Medical Dictionary for Regulatory Activities MedDRA version 23.0.

An overall summary of TEAEs, including the number of events reported, the number and percentage of participants reporting at least one TEAE, the number and percentage of participants discontinuing due to an adverse event, the number and percentage of participants with at least one serious adverse event, and the number and percentage of deaths will be presented.

The most frequent adverse events ($\geq 5\%$) will be compared between the INOpulse and placebo groups using a forest plot. The forest plot will display odds ratios of the incidence rate for each AE along with 95% confidence intervals.

A table of all anticipated and unanticipated deaths due to any cause, with number and frequency of such events in each arm/group of the clinical study, as well as the number of occurrences for each event. This also requires notification if the death is causally related to treatment for each reporting group.

A breakdown of the number and percentage of participants reporting each adverse event, categorized by System Organ Class (SOC) and preferred term (PT), will be presented. Note that counting will be by participant not event and participants are only counted once within each SOC and PT.

A further tabulation of these data, categorized by relationship to INOpulse, will be presented. Participants with multiple events within a particular body system or preferred term will be counted under the category of their drug-related event (related and not related) within SOC and PT. Relationship to INOpulse is categorized as related (rated "possible" or "related" in the CRF) or not related (rated "unlikely" or "not related" in the CRF).

A summary of events reported, categorized by severity, will also be provided. Participants with multiple events within a particular SOC and PT will be counted under the category of their most severe event in the following order: severe > moderate > mild within that SOC and PT.

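### Protocol 13.2.2 counts a disease explanation towards *Possibly related* and leaves an event with good timing, no disease explanation and no known drug pattern without a category

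*Protocol*

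**What the plan says.** Protocol 13.2.2 gives investigators four ratings.

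- *Not related* is for events that are beyond doubt due to something else.
- *Unlikely related* has two bullets: timing that makes a link improbable, and "Disease or other drugs provide plausible explanations". Nothing says whether one bullet is enough.
- *Possibly related* applies "if it meets at least 2 of the following criteria". Two of the three are a plausible time relation to dosing and a known response pattern. The other, listed between them, is "It may readily have been produced by the subject's clinical state or by environmental or toxic factors".
- *Related* requires all four of its criteria: timing, no reasonable explanation in the subject's clinical state, a known pattern, and "It reappears upon re-challenge". The text beneath this heading calls the category probably related, which is not one of the listed ratings.

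Protocol 13.1.4 sets a separate standard for a suspected adverse reaction: "there is a reasonable possibility that the investigational product caused the AE". It adds that this means evidence suggesting a causal link.

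SAP 13.6.2 reduces the four ratings to two ("Relationship to INOpulse is categorized as related" for the possible and related ratings; unlikely and not related form the other group). A participant with several events in the same class or term is counted under the drug-related one.

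**The concern.** A plausible alternative cause normally weakens the case for a drug effect. Section 13.2.2 treats it that way under *Related* and *Unlikely related*, but under *Possibly related* it adds a point towards relatedness. In hospitalized COVID-19 patients most complications have an obvious disease explanation, so the reversed criterion will often be in play. Serious events are affected too: "If the subject develops respiratory failure, as defined in this protocol, it will be considered an SAE".

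Four outputs use the rating:

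- SAP Table 14.3.2.6, adverse events by relationship;
- the SAP 13.6.2 notification of whether a death is causally related;
- the protocol's interruption wording, which refers to product-related adverse events;
- the investigator's input to the sponsor's judgement on suspected reactions.

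If the categories overlap or leave gaps, the related column partly reflects how each site resolves the wording.

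**Working it through.** The documents give no figure to reproduce here. The check applies the 13.2.2 rules to every combination of four yes/no attributes:

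- T: reasonable timing;
- C: readily explained by the clinical state;
- P: known response pattern;
- R: reappears on re-challenge.

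Two simplifications: the slightly different alternative-cause phrases in the three categories are all treated as C, and the *Unlikely* timing bullet is treated as not-T.

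**Rules**

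- *Possibly*: T + C + P ≥ 2.
- *Related*: T, not-C, P and R all true.
- *Unlikely*, either bullet enough: not-T or C.
- *Unlikely*, both bullets needed: not-T and C.

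**Events with reasonable timing (T = 1)**

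| C | P | Score | *Possibly* | *Unlikely* (either) | *Unlikely* (both) | *Related* |
|---|---|---|---|---|---|---|
| 1 | 0 | 2 | yes | yes | no | no |
| 1 | 1 | 3 | yes | yes | no | no |
| 0 | 1 | 2 | yes | no | no | only if R = 1 |
| 0 | 0 | 1 | no | no | no | no |

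The first and last rows differ only in whether disease explains the event. The disease-explained event qualifies as *Possibly related*. The unexplained one fits none of these three categories, and it is not *Not related* either, because no other cause has been established beyond doubt.

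**Counts over all 2 × 2 × 2 × 2 = 16 combinations** (logical combinations, not event frequencies)

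- *Possibly* is met by 8.
- If either *Unlikely* bullet is enough, 6 of those 8 also meet *Unlikely*: 4 with T = 1, C = 1 and 2 with T = 0, C = 1, P = 1.
- If both bullets are needed, the overlap falls to the last 2, and no event with reasonable timing is *Unlikely*.
- *Related* is met by 1 (T = 1, C = 0, P = 1, R = 1). With R = 0 it is never met.

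**Effect on the SAP split.** Where *Possibly* and *Unlikely* overlap, the two available ratings fall on opposite sides, and neither document has a tie-break. The re-challenge requirement does not move the split: an event with T = 1, C = 0, P = 1, R = 0 misses *Related* but scores 2, is *Possibly related*, and is still tabulated as related.

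**Testing two simple repairs**

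- Delete the clinical-state criterion and keep at least two: T and P both become mandatory. The unexplained event with no known pattern (T = 1, C = 0, P = 0) scores 1 and is still excluded.
- Reverse the criterion, so the score is T + (1 − C) + P: the disease-explained event with no pattern falls to 1 and the unexplained one rises to 2. But T = 0, C = 0, P = 1 also scores 2 and still meets the *Unlikely* timing bullet if one bullet is enough. Reversal alone does not separate the categories.

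**The case against.** **Discretion.** Both middle categories are worded permissively, and *Not related* remains open for an event that is plainly due to COVID-19. An investigator is not forced to call such an event *Possibly related*. This stands, and it means the documents do not show that most on-treatment complications will be rated related; they give no attribution frequencies. It does not remove the reversed criterion, since investigators are told to use these explanations.

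**The overlap is one reading.** If the two *Unlikely* bullets must both hold, it disappears for events with reasonable timing. This stands, so the overlap is stated conditionally. The gap for unexplained events is present on either reading.

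**Re-challenge.** A reader might infer that a clear drug effect such as high methemoglobin can never be rated *Related*. The documents do not support that. Protocol 10.1.12 interrupts treatment first and lets the investigator restart it, so recurrence could be seen, and 10.1.14 also provides for restart after symptomatic rebound. On a strict all-four reading, the bar applies to fatal events and to those with no restart.

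**Safeguards.** A reader might infer that drug signals will be buried. The main safety tables are all-cause. All respiratory events and methemoglobin of 7% or more are of special interest whatever their attribution. An unblinded DMC reviews adverse events by arm at least monthly. Sites report every serious event within 24 hours whether or not it is associated with the product, and 13.1.4 and 13.1.8 give reporting its own standard. Ratings are blinded and follow one rule in both arms. This stands and limits the impact, but it does not correct the relationship table.

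**Conclusion.** The point holds as a minor wording defect with a definite logical consequence. In 13.2.2 a disease explanation raises an event with reasonable timing and no known pattern into *Possibly related*; without that explanation the same event has no category. The overlap with *Unlikely* holds only if one bullet is enough. The re-challenge requirement, read strictly, largely empties *Related* but leaves the SAP split unchanged.

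The number of misattributed events cannot be estimated from the documents. A reader might take the SAP planning rates, 0.15 × 250 + 0.06 × 250 = 37.5 + 15 = 52.5 subjects with death or respiratory failure, and conclude that the related count could lie anywhere from 0 to about 53. That is only a logical bound. It needs every site to choose the same category, every event to have reasonable timing, and the one-bullet reading of *Unlikely*.

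The damage is limited to the four outputs that use attribution. The primary and secondary efficacy endpoints, the endpoint of adverse events leading to discontinuation (SAP 13.6.2 identifies these by the action taken on study drug) and the futility rule do not use causality.

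**What to change.** Amend Protocol 13.2.2:

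1. Define the cut between *Possibly* and *Unlikely* by the 13.1.4 standard: is there a reasonable possibility that the product caused the event, yes or no. This makes the two categories mutually exclusive.
2. Stop counting a clinical-state explanation towards relatedness, and revise the two-of-three threshold in the same edit, so that reasonable timing without a disease explanation can qualify even when no drug pattern is known.
3. State whether any or all of the *Unlikely* bullets are needed.
4. Make re-challenge a supportive criterion for *Related*, considered if it was performed. This changes only how causality is rated and asks for no restart of treatment.
5. Reconcile the heading *Related* with the text that calls it probably related.

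The two-group mapping in SAP 13.6.2 can stay. The cost is protocol wording, CRF completion guidance, a short site training note, and blinded queries for events already assessed. No new data are needed.

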13.3. Outcome Assessment for Adverse Events

The outcome assessment for an AE will be defined as follows:

- Fatal
- Not recovered/not resolved
- Recovered/resolved
- Recovered/resolved with sequelae
- Recovering/resolved
- Unknown

Pregnancy occurring in a subject is not considered an AE or SAE; however, the Investigator must collect pregnancy information for female study subjects or female partners of male study subjects if the fetus could have been exposed to the investigational device. Any pregnancy should be reported to the Sponsor using the Serious Adverse Event Report Form (SAE Report Form). Delivery details and the neonatal outcome must be recorded and reported.

13.4. Collection, Recording and Reporting of Adverse Events and Investigational Product Complaints/Deficiencies

13.4.1. Collection of Adverse Events and Serious Adverse Events

Any AE occurring prior to signing the ICF should be considered medical history or a pre-existing condition, and will be collected on the Medical History eCRF. Findings at Screening from physical exam, baseline laboratory results, etc. should also be considered medical history or pre-existing condition and be recorded accordingly.

At each visit, the Investigator will determine whether any AE has occurred and if it is related to the investigational product. Subjects will also be instructed to contact the site to report any AE that occurs between study visits. For randomized subjects, AEs and SAEs will be collected from signing of the ICF through the EOS and entered on the AE section of the eCRF.

SAEs (including those related to investigational product complaints/deficiencies) occurring from signing of the ICF at screening run in through the EOS will be reported to Bellerophon Pulse Technologies Drug and Device Safety Department or their designee within 24 hours of an Investigator becoming aware of the event, using the AE/SAE page in the eCRF.

As laboratory abnormalities may fall into the category of expedited reporting, the Investigator will review the clinical laboratory test results in a timely fashion. Only those results qualifying as AEs/SAEs will be recorded in the AE section of the eCRF.

Adverse events will be coded according to the most current version of MedDRA. All medical device deficiencies associated with a SAE will be coded and reported as required.

13.4.2. Collection of Investigational Product Complaints/Deficiencies

Information is collected on investigational product complaints/deficiencies from the Investigators. An investigation of an investigational product complaint/deficiency is performed to determine the root cause by the Sponsor. This will include evaluation of the reported complaint details, and data from the device service log when downloaded by the Sponsor. Details of collection of investigational product complaints/deficiencies will be provided to the sites in a separate site instruction. In the case of a device deficiency and upon request of the Sponsor, the remaining investigational product study materials must be returned to the Sponsor and/or their designee for further investigation.

13.4.3. Serious Adverse Events and Medical Device Deficiency Reporting

The Sponsor shall be responsible to submit all appropriate documentation to all governing Health Authorities in accordance with local laws, regulations, and standards.

Any SAR that is both serious and unexpected will be considered reportable for the investigational product and will be handled as such by the Sponsor.

The following events will be considered reportable for the investigational product and will be handled as such by the Sponsor:

1. Any associated with an SAE
2. Any investigational medical device deficiency that might have led to an SAE if:
 - a. suitable action had not been taken; or
 - b. intervention had not been made; or
 - c. if circumstances had been less fortunate
3. New findings and/or updates in relation to already reported events
4. Any events that require remedial action

Notification of any SAE or investigational medical device deficiency, whether or not associated with the drug or device, by Investigators to the Sponsor is required **within 24 hours**. The reporting of SAEs or investigational medical device deficiencies will be conducted in accordance with ICH E2A (Clinical Safety Data Management: Definitions and Standards for expedited reporting) and local regulatory guidelines.

Any SAE must be reported using the SAE form at the study site **within 24 hours** of the site staff becoming aware of the event or investigational medical device deficiency.

The initial SAE report should include a detailed description of the event including start and stop dates, relationship, severity, and outcome assessments by the Investigator. All necessary information including laboratory test results and diagnostic information should also be provided

when reporting the SAE or providing follow-up. Follow-up information (including information requested by the Sponsor) should be reported within 24 hours of availability. Any additional supporting documentation should be faxed to:

Pharmacovigilance Dept.
[contact]
Email: [contact]

If you have specific questions regarding the reporting of SAEs, you should contact the local Medical Monitor.

13.4.3.1. Site Reporting to IRB/IEC

The Investigator must also notify the local IRB/IEC which approved the study of any SAEs, AEs, or device deficiencies, in accordance with local health authority guidelines.

13.4.3.2. Sponsor Reporting to Regulatory Authorities, Investigators, and Independent Ethics Committee

The Sponsor will notify the relevant Regulatory Authorities and all participating Investigators of reports of potential safety risks from clinical studies or any other source, in accordance with applicable regulations. Upon notification of an event, the Sponsor will determine the need for reporting and the timeline for reporting in each active country. The reporting of SAEs will be conducted in accordance with ICH E2A (Clinical Safety Data Management: Definitions and Standards for expedited reporting) and local regulatory guidelines.

Upon request, the Sponsor shall report the results of device deficiency evaluations to Regulatory Authorities and participating Investigators. Where applicable, Investigators will submit this information to their local IRB/IEC.

All AEs, SAEs, and device deficiencies will be reported to the regulatory authorities and IECs in accordance with the current country specific regulatory and IRB/IEC requirements. These will be outlined in the Safety Management Plan for this study.

13.5. Data Monitoring Committee

An independent DMC will monitor and review data periodically throughout the trial, at a minimum monthly, as described in the DMC charter (Version 6.0 07 July 2020). The DMC will alert the Sponsor if there is any safety concern based on the provided data and will also advise on the appropriateness of continuing the study based on the DMC charter and in accordance with the statistical analysis plan. All SAEs will be sent to the DMC in a timely manner for review. A DMC charter will be developed with input from the DMC committee members, the SC and the Sponsor.

